#### **D. Research Population & Recruitment Methods**

We anticipate the sample to be comparable with community demographics in each of the testing regions within the counties participating in this study. As we are specifically conducting outreach to encourage Latinx individuals to attend testing events, we expect the overall study population to be 85% Hispanic and 15% non-Hispanic, with 84% of individuals identifying as Caucasian in both ethnic groups and the remaining 16% identifying as African American, Asian, Pacific Islander,

American Indian/Alaska Native, or more than one race. We expect a slight excess of female participants, based on the demographics in the standing population.

- 1. De-identified protected health information participants** will include data from all testing sites participants which will include individuals age 3 and older. We expect approximately 900 people per week will attend a testing event and we will assess outcomes over 40 weeks, thus we expect between 32,000- 36,000 individuals will be included in the testing. Individuals will not be directly recruited to provide these data.
- 2. Individual level survey data** will include participants who are (a) age 15 years and older; (b) attending an NIH-funded testing event. Exclusion criteria include: (a) individual is unable to understand Spanish or English or another language translated by a qualified translator at a 5th grade level (participants who cannot read will have the consent or assent form read to them); (b) individual discloses that they previously enrolled in the research project. We anticipate up to 3,600 adult individuals will provide survey data. Up to 1,800 individuals will be individuals who had received the promotores intervention and up to 1,800 will have received services as usual. Recruitment will occur at the testing site, by a study research assistant. A standardized recruitment script (see recruitment information document) will be used and will include eligibility questions. Participants will be compensated with a \$30 gift card for each survey they complete (one at baseline, one at one month follow-up for a total of \$60 in gift card renumeration available). To recruit participants, we will also add the following text to testing event flyers circulated by our community partners '\$30 gift cards available for those eligible to participate in a research survey.'
- 3. Anonymous participant interview** will be collected from a sub-set of randomly selected individuals at NIH-funded testing events who are age 18 years or older. We will invite approximately 15 individuals to participate in a brief anonymous interview (5-8 open-ended questions) with a study staff member at our testing events. Anonymous interview data will assist with informing the study about individual behaviors related to attending testing events. We will audio record these interviews for transcription. All audio recordings will be destroyed after transcription activities are complete. A standardized recruitment script will be used, which will provide information about the purpose of the interview and permission for audio recording. Individuals will be compensated with a \$15 gift card for completion of this interview. These anonymous interviews will not be used as research data, and are only to provide feedback on the testing events. This aspect of the study has now been completed.
- 4. Promotores activities.** Promotores will be recruited after receiving contact information from the community-based organization employing each promotor. They will be invited to participate in the promotores training and, for NIH-funded testing events, they will be asked to complete the informed consent and survey asking about their demographics and personality during the course of the promotores training. Promotores will also be invited to participate in a focus group interview about their experiences delivering the intervention and opinions on the project and content delivery. There is no monetary incentive for participation. The only inclusion criteria will be that the individual must be a promotor funded by the present study.
- 5. Community Based Organization general outreach activities.** A monthly email will be sent to the executive director of each CBO participating in the NIH-funded testing events to complete a survey on general outreach activities. Completion of the survey is part of the requirements for receiving CBO funding.

For data analysis, we will employ standard normal theory generalized linear modeling analysis of covariance fractional factorial analyses using pre-post assessment scores for site and individual level outcomes.

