## B. Specific Aims/Study Objectives

The overall goal of our proposed research is to implement a culturally-tailored community outreach and testing program to increase the reach, access, uptake, and impact of testing in Latinx communities in Oregon. This project will fully integrate with the NIH Rapid Acceleration of Diagnostics (RADx) consortium and its Coordination and Data Collection Center (CDCC). With guidance and leadership from our Latinx Community and Scientific Advisory Board, we will launch the proposed testing program which will result in 36 community testing sites to serve Latinx communities. For the proposed research activities, we will test the following questions:

- 1) Do culturally-informed interventions ('Promotores') increase test rates and health behaviors?
  - a. Community-level intervention to increase participation in testing: Evaluate whether 'Promotores de Salud,' a culturally-tailored outreach intervention that includes psychoeducation, information support, and motivational strategies to address barriers, results in more tests completed and more sites testing at full capacity, as compared to basic community-level outreach services.
  - b. Individual-level booster intervention to change future health behavior: Examine whether a brief, individual-level 'Promotores de Salud' intervention held during a testing event (compared to distribution of a pamphlet only) results in greater use of strategies that reduce transmission at the community and individual level. Individual moderators (e.g., substance use, perceived threat, health literacy, social determinants) will also be examined. We further hypothesize that this intervention will increase future test rates through repeat testing visits and

through ‘snowball’ recruitment of friends and family to attend future testing events.

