## C. Methods, Materials and Analysis

Overall Study Design: We will partner with community organizations to administer SARS-CoV-2 tests at organized, planned testing events located in communities across Oregon. Sample collection will occur in counties across Oregon and we will collaborate with county public health agencies to determine sites. Samples will be collected using services as usual using a standardized intake form and standardized, EUA authorized sample collection approaches. Data used to evaluate the efficacy of interventions will involve de-identified participant data at the level of the testing site. This study is a randomized clinical trial to test whether ‘Promotores,’ community health workers who deliver culturally-informed set of outreach, education, and engagement interventions, will result in an increase in testing utilization and health behaviors in Latinx communities.

Randomization will occur at the site level such that 18 sites will be randomized to receive the Promotores intervention and 18 will be randomized to receive services as usual. Services as usual include outreach by county public health and community-based organizations (fliers, radio ads, social media, etc.). The promotores intervention includes targeted outreach to Latinx community members and educational direct interactions with participants and distribution of a pamphlet, with the goal of increasing health behaviors and encouraging additional/future testing. The UO will provide support to community-based organizations to employ and train these promotores to assist with recruitment. The promotores will include Spanish speakers, across cultural contexts, living and working in, and intricately connected to, the target community.

- **Outreach as usual description**
  - Basic outreach materials document (flyers, social media posts, radio announcements, etc.)
  - Flyer to promote health behaviors
  - These documents may be modified or not used at all by community stakeholders as they may have other documents they are already using for outreach and health education—these materials are intended to be used for counties who do not have existing or preferred materials
  - See 04c.Services as Usual Materials
- **Promotores intervention description**
  - Basic outreach and flyer to promote health behaviors plus the outlined outreach and health behaviors promotores approaches
  - Promotores training will be provided by the study team
  - See 4d. Promotores Training Outline

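### The individual pre score is taken at the testing event, after randomisation and outreach, so the protocol's analysis of covariance cannot estimate the effect of the whole Promotores package on health behaviour

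*Protocol*

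**What the plan says.** Protocol section C allocates whole sites: "Randomization will occur at the site level such that 18 sites will be randomized to receive the Promotores intervention", and 18 others receive services as usual. What is allocated is one package: "The promotores intervention includes targeted outreach to Latinx community members and educational direct interactions with participants and distribution of a pamphlet". Section C also has community organisations "employ and train these promotores to assist with recruitment". Section B describes the outreach as more than publicity. It is an "outreach intervention that includes psychoeducation, information support, and motivational strategies to address barriers".

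Section B asks two questions. Question 1a concerns outreach and the number of tests completed. Question 1b concerns a brief on-site contact, compared with a pamphlet alone, and later health behaviour.

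On the survey, section D states: "Recruitment will occur at the testing site, by a study research assistant". Section C has the first survey done in person at the event and the second a month later. No earlier survey is described. Section D describes the intervention half of the survey sample as "individuals who had received the promotores intervention".

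The analysis is given in one sentence at the end of section D: "analysis of covariance fractional factorial analyses using pre-post assessment scores for site and individual level outcomes". The SAP (4.3) has no Promotores-versus-usual comparison of survey scores. Its Aim 1 model has no pre score, and its Aims 2 and 3 model change within the intervention group.

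**The concern.** Analysis of covariance estimates a treatment effect cleanly when the covariate was fixed before treatment could act on it. Here the covariate comes after allocation and after one of the two parts of the treatment. If outreach has already changed mask use, distancing or similar reports by the day of the event, the adjusted comparison credits that change to the baseline and not to the intervention. If the survey also follows the on-site contact, part of the booster effect is lost as well.

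The section D sentence is the only stated method for comparing the arms on health behaviour. As written, its result could be read as the package effect or as the booster effect, and the plan does not say which is meant.

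**Working it through.** **Order of events for a survey participant at an intervention site (Protocol sections B, C, D).** Site randomised; outreach in the community; person attends; survey and on-site contact, in unstated order; second survey at one month. The pre score therefore follows randomisation and outreach under either order.

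**The plan's own count.** SAP 4.3 (Aims 2 and 3 Power): 300 tests per month × .50 enrolment × 11 months = 1,650; 1,650 × .50 retention = 825. This reproduces. The figure belongs to the SAP's within-intervention design and is not in dispute; only its 50% retention is used below.

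**Bias.** Let T be the total effect at one month, a the shift outreach has already caused in the pre score, and b the within-arm slope of the one-month score on the pre score. With comparable attendees in the two arms:

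adjusted effect = T − b × a, so bias = −b × a.

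Neither a nor b is in the documents. Assume a = 0 to .3 SD and b = .5 to .7.

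| Shift a (SD) | Bias size, b = .5 | Bias size, b = .7 |
|---|---|---|
| 0 | 0 | 0 |
| .1 | .05 | .07 |
| .2 | .10 | .14 |
| .3 | .15 | .21 |

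**Yardstick.** Inputs: up to 1,800 survey participants per arm and 18 sites per arm (Protocol); 50% retention, power .80, alpha .05 and an individual-level intraclass correlation (ICC) of .30 (SAP). A two-sided test is assumed, with no precision gain from covariates.

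- Completers per arm: 1,800 × .50 = 900; per site: 900 / 18 = 50.
- Design effect: 1 + 49 × .30 = 15.7.
- Standard error: √(2 × 15.7 / 900) = .187 SD.
- Detectable effect on 34 df: (2.032 + .852) × .187 = .54 SD.
- Largest bias as a share: .21 / .54 = 39%. For a = .1 and b = .5: .05 / .54 = 9%. For a = 0: none.

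**Simulation** (36 sites, 50 completers each, assumed ICC .05, T = .30, b = .5, 400 replicates):

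| Situation | Without pre score | With pre score |
|---|---|---|
| No shift, no selection | .294 | .299 |
| Outreach shift +.15 | .296 | .225 |
| Attendees differ by +.15, no shift | .377 | .301 |
| Attendees differ by −.15, no shift | .225 | .300 |
| Shift +.15 and attendees −.15 | .225 | .226 |

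Row 2 agrees with the formula: .30 − .5 × .15 = .225, a loss of 25%. Rows 3 and 4 show the opposite case: when outreach changes who comes and not how they behave, adjustment removes the bias. In row 5 the observed pre scores balance, yet both models are wrong.

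**Power.** With a normal approximation and the same 900 per arm, a fall in the effect from .30 to .225 lowers power from .36 to .23 at ICC .30, or from .93 to .73 at an assumed ICC of .05.

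**A related inconsistency.** Protocol section G has half of those at an intervention site being offered the intervention, which does not fit the allocation of whole sites in section C. The two must be reconciled. The figures above follow section C.

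**The case against.** The strongest reply is that question 1b is the health-behaviour question and concerns only the on-site contact. For that target, a score taken at the event before the contact is a proper baseline, and adjusting for it removes none of the booster effect. This stands. It depends on the survey coming first, which the supplied text does not fix; the training outline and recruitment documents it refers to might. Section C also randomises outreach and contact together, so the package remains a natural target.

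The second reply is that the event-day score guards against differences in who attends, which outreach itself influences. This also stands, and it is why simply dropping the score is no cure.

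A reader might infer more than the documents support:

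- *That adjustment must shrink the effect.* It does so only if outreach had moved the measured behaviours by the day of the event. Section B makes that plausible, but nothing shows it. With selection, the direction of any error depends on the case.
- *That the survey follows the contact because section D says "individuals who had received the promotores intervention".* The phrase labels an arm in a planned count. Section D also calls the first survey the baseline, and SAP 4.3 treats its baseline as preceding Promotores.
- *That the bias could consume most of a detectable effect.* With an ICC of .05 to .10 the detectable effect would be .25 to .33 SD, and .21 would be a large share of it. Those values are not in the documents. The only individual-level ICC given is .30, for testing outcomes; none is given for behaviour scores.
- *That the primary outcome is affected.* The section D sentence names site outcomes too, but a survey score is no baseline for testing counts. The gap there is a different one: no site-level pre-period is defined.

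**Conclusion.** The point holds for individual health-behaviour outcomes in the site-randomised comparison. The planned analysis of covariance cannot estimate the total effect of the package, because its covariate is measured after allocation and outreach. It can estimate the booster effect only if the survey precedes the on-site contact. Even then, that reading requires comparable attendees, or differences captured by the score, and no route from outreach to the one-month score that bypasses the event-day score.

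The size is conditional: 0 to .21 SD, at most about 39% of a detectable effect of about .54 SD. This rests on the assumed shift and slope, 50% retention of 1,800 per arm, and use of the SAP's ICC of .30 for behaviour scores. The Aim 1 model and the within-intervention models of Aims 2 and 3 in the SAP are untouched.

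**What to change.** 1. In the field procedure, require the first survey before any on-site Promotores contact, at the same point of the visit in both arms.
2. In the analysis plan, label the model adjusted for the event-day score as the increment due to the on-site booster. Report beside it a package-effect model adjusted only for items outreach cannot change: age, sex, ethnicity, site census characteristics and calendar time. Compare attendee characteristics by arm, so that the two results can be read together.

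The cost is one procedural line, some analysis wording and a little more analysis. The model without the event-day score is less precise and open to selection bias from who attends. The model with it cannot show what outreach achieved before the event. Neither alone is a full cure, which is why both should be reported.

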## E. Informed Consent Process

**1. De-identified protected health information participants.** We will not obtain informed consent for using de-identified testing data. Informed consent will not be obtained as processes and procedures will occur as usual for sample collection and we will only receive limited protected health information from the CLIA laboratory. We are requesting a complete waiver of informed consent for this aspect of the research.

- The research involves no more than minimal risk to the subjects because the data collected will not be identifiable
- The research could not be practicably carried out without the waiver, because asking participants to complete the informed consent process would substantially increase the length of time required for testing and would result in fewer resources available for testing
- While the research uses HIPAA identifiers, it does not include identifiable patient information (see HIPAA 4a)
- The waiver will not adversely affect the rights and welfare of the subjects as data provided to the study team will not be identifiable
- There is not a need to provide additional pertinent information after participation

**2. Individual level survey data** We will use a standardized consent form to consent participants 18 and older at NIH-funded testing events. Individuals between the ages of 15-17 at NIH-funded testing events will use a standardized assent form to agree to participate. All individuals will read the consent or assent form and will be asked if they have any questions. For individuals who do not speak English or Spanish, a translator may be available in some instances. Individuals over 18, who cannot read at a 5th grade level will have the consent form read to them. When appropriate, translators will be available for individuals in the Latinx community who speak languages other than English or Spanish, such as Mam. Children will never be used as translators.

The assent form is at a 6th grade reading level and is in plain language. Any questions will be answered by the research staff.

We are requesting a waiver of parental consent to allow individuals between the ages of 15-17.99 to participate in this research study. The age of medical consent in Oregon is 15, so COVID-19 testing is available at our events to individuals 15 years of age and older without parental consent. Because of this, many individuals between the ages of 15-17.99 come to COVID-19 testing events without a parent present. We are requesting to seek their assent, and not consent of their guardian.

- The research involves no more than minimal risk to the subjects because the data collected will not be identifiable
- The research could not be practicably carried out without the waiver, because asking the guardian of participants age 15 – 17.99 to complete the informed consent process would substantially increase the length of time required for testing and would result in fewer resources available for testing
- The waiver will not adversely affect the rights and welfare of the subjects as data provided to the study team will not be identifiable
- There is not a need to provide additional pertinent information after participation

Participant consent or assent will include consent or assent to share protected health information from the University of Oregon's CLIA certified laboratory, with the study team, so we can link testing intake data with participant survey data. During the informed consent and assent process, participants will be informed that their personally identifiable information is being collected to link testing intake data with their survey data and to be able to understand how well we are reaching people who identify as Latino/a/x in a community.

Participants will be assured that their participation in the study is voluntary and that if they choose to participate, they can change their minds at any time. They will be informed about potential benefits and harm. They will be informed that their decision about whether to participate will not alter the medical care, or social services they will receive at any time from the county partners and that they will not be denied services of any kind. Participants over 18 years old will be asked to sign an informed consent form that explains the project, their rights, and how the data will be used in the future. Participants between the ages of 15-17 will sign an assent form that explains the project, their rights, and how the data will be used in the future. A phone number and email address linking participants to Spanish-speaking and English-speaking members of the research team will be provided so participants can contact project staff if they have any questions about the consent or assent form. Translation services may be leveraged if a participant does not speak either language. Research assistants will be trained in recruitment procedures and have specialized training in how to handle any exceptions. The random assignment component of the study will be carefully explained and it will be made clear that the randomization will not affect the SARS-CoV-2 testing procedure or the reporting of results. We have used similar consent and assent procedures in many prior intervention research studies and have successfully recruited large numbers of participants in community agencies.

At the time of consent or assent, the research staff will review the consent or assent form with the participant before they sign it to ensure that the participant is clear about data will be obtained by National Institutes of Health and Duke Clinical Research Institute versus the UO. The research staff will also clarify that the identifying information that the participant includes in the CDE survey will be used by National Institutes of Health (NIH) and Duke Clinical Research Institute (DCRI) to link to other data such as Medicaid data, though once linked the data will be de-identified. The research assistant will also clarify that Medicaid and other data to which NIH/DCRI links will not be used by UO. Participants will be presented with the consent or assent to participate in the survey. Following that agreement, by obtaining a typed name, participants will be invited to link intake data and test result to the survey and core elements of a HIPAA authorization will be presented. A signature will be collected for the HIPAA Authorization (typed and finger drawn). Refusal to allow linking of intake and test result is not an exclusion criterion.

An informed consent form and assent form will be posted on a Federal Web site (e.g., [clinicaltrials.gov](https://clinicaltrials.gov)) after the clinical trial is closed to recruitment, and no later than 60 days after the last study visit by any subject.

**3. Anonymous participant interview.** We will not obtain documentation of informed consent from participants to complete this interview. Instead participants in NIH-funded testing events will be asked to verbally agree to participate in the anonymous interview. Therefore, consent will be solicited from participants verbally, and there will not be documentation of their consent. Thus, we are requesting a waiver of documentation of consent for this component of the research, to allow for a verbal consent process. Verbal consent to participate will be received prior to starting the interview. This aspect of the study is now complete.

- The research involves no more than minimal risk to the participants because the data collected will not be identifiable
- The waiver will not adversely affect the rights and welfare of the participants as data provided to the study team will not be identifiable
- There is not a need to provide additional pertinent information after participation
- Participants will be asked to verbally consent to completing the interview, after 1) being informed that this is a research study; 2) given a description of foreseeable risks and discomforts of participating; 3) provided contact information for the Project Coordinator, should they have questions.

**4. Promotores activities.** We will use standardized consent forms to consent participants in NIH-funded testing events. All individuals will read the consent form and will be asked to reach out to the study team if they have any questions. The consent forms will be programmed in Qualtrics. The Qualtrics links will be provided to Promotores by email. Promotores will sign their name, type their name, and provide the date to indicate informed consent. Promotores will be invited to share information about their demographics and personality, as well as participate in a focus group to share their experiences and opinions on the intervention. Sharing this information is optional.

**5. Community Based Organization general outreach activities.** Consent is not required for this activity because we are collecting data on the organization activities, rather than individual behaviors or impressions.

